10.5 Other Required Reporting

10.51 All adverse events should be graded at each evaluation per the CTCAE v4.0 grading.

10.52 Submit via appropriate Academic and Community Cancer Research United (ACCRU) Case Report Forms (i.e., paper or electronic, as applicable) the following AEs experienced by a patient and not specified in Section 10.5:

10.521 Grade 2 AEs deemed *possibly, probably, or definitely* related to the study treatment or procedure.

10.522 Grade 3 and 4 AEs regardless of attribution to the study treatment or procedure.

10.523 Grade 5 AEs (Deaths)

10.5231 Any death within 30 days of the patient's last study treatment or procedure regardless of attribution to the study treatment or procedure.

10.5232 Any death more than 30 days after the patient's last study treatment or procedure that is felt to be at least possibly treatment related must also

be submitted as a Grade 5 AE, with a CTCAE type and attribution assigned.

10.53 Refer to the instructions in the Forms Packet (or electronic data entry screens, as applicable) regarding the submission of late occurring AEs following completion of the Active Monitoring Phase (i.e., compliance with Test Schedule in Section 4.0).

10.54 Non-Serious Adverse Events (NSAEs) Collecting and Reporting

The collection of non-serious adverse event (NSAE) information should begin at initiation of study drug. Non-serious adverse event information should also be collected from the start of a placebo lead-in period or other observational period intended to establish a baseline status for the subjects.

Non-serious AEs should be followed to resolution or stabilization, or reported as SAEs if they become serious. Follow-up is also required for non-serious AEs that cause interruption or discontinuation of study drug, or those that are present at the end of study treatment as appropriate.

Non-serious Adverse Events will be provided to BMS via the reconciliation report as outlined below.

10.55 Reconciliation

The Research Coordinating Center will reconcile the clinical database SAE cases transmitted to BMS Global Pharmacovigilance (GPV&E). Reconciliation will occur every three months and once just prior to database lock/Final Study Report (FSR). BMS GPV&E will e-mail upon request from the Research Coordinating Center, the GPV&E reconciliation report. The data elements listed on the GPV&E safety data reconciliation report will be used for case identification purposes. If the Research Coordinating Center determines a case was not transmitted to BMS GPV&E, the case will be sent immediately.

11.0 Treatment Evaluation Using RECIST Guideline – Not applicable

12.0 Descriptive Factors – Not applicable

13.0 Treatment/Follow-up Decision at Evaluation of Patient

13.1 A patient is deemed *ineligible* if after registration, it is determined that at the time of registration, the patient did not satisfy each and every eligibility criteria for study entry. The patient may continue treatment off-protocol at the discretion of the physician as long as there are no safety concerns, and the patient was properly registered. The patient will go off study.

- If the patient received treatment, all data up until the point of confirmation of ineligibility must be submitted.
- If the patient never received treatment, on-study material must be submitted.

13.2 It is deemed a *major violation*, if protocol requirements regarding treatment of the patient in cycle 1 of the initial therapy are severely violated that evaluability for primary end

point is questionable. This determination needs to be made by an investigator blinded to treatment allocation.

- 13.3 It is deemed a *cancel* if the patient is removed from the study for any reason before any study treatment is given. On-Study material and the End of Active Treatment/Cancel Notification Form must be submitted. No further data submission is necessary
- 13.4 If the patient meets criteria for a major bleed, they will have met a major safety endpoint and will be removed from the study. All data up until the point of major bleed should be entered. The patient will then be managed as appropriate per the clinical situation and current guidelines.
- 13.5 If the patient meets criteria for a recurrent venous thromboembolic event, they will have met a major secondary endpoint and will be removed from the study. All data up until the point of a recurrent venous thromboembolic event should be entered. The patient will then be managed as appropriate per the clinical situation and current guidelines.
- 13.6 If the patient suffers a non-major clinically relevant bleeding event, they will have met a major safety endpoint. Medical management will be provided in accordance with the location and severity of the bleeding event. This may include temporary cessation of study medication. Once the bleeding event has been appropriately managed, they will restart study medication and will be followed appropriately per protocol. They will not be removed from the study for this event.
- 13.7 Disease progression is not a reason for stopping the study medication. If the patient goes on hospice, they may continue the study medication and the protocol procedures. If it is decided that the patient is too ill to stay on the study, then it can be stopped.

14.0 Body Fluid Biospecimens – Not applicable

15.0 Drug Information

- 15.1 Apixaban (Eliquis®) IND #134645

Review the investigator brochure, available on the ACCRU web site, for the most current and complete adverse event information.

- 15.11 Background: Apixaban (Eliquis) is an oral direct factor Xa inhibitor which impairs coagulation by inhibiting the conversion of prothrombin to thrombin. It does not require antithrombin for antithrombotic activity and inhibits both free and clot-bound FXa. Apixaban has an apparent half-life of about 12 hours and thus is dosed twice-daily. Bioavailability is approximately 50% after oral dosing with maximum concentrations at 4 hours post ingestion. The pharmacokinetics are linear and plasma protein binding in humans is high at nearly 90% with a volume of distribution of approximately 20 liters. Apixaban is metabolized in the liver mainly via the CYP3A4 pathway. Renal excretion accounts for about 27% of total clearance. Approximately 25% of the drug is eliminated in the feces. This drug is not dialyzable due to its high plasma protein binding. Apixaban is currently FDA approved for prevention and treatment of venous thromboembolism and stroke prevention in the setting of non-valvular atrial fibrillation.

15.12 Formulation: Apixaban (Eliquis®) tablets are available for oral administration in strengths of 2.5 mg and 5 mg of apixaban. Both tablets have the appearance of Reddish brown, plain, oval shaped, shallow biconvex film coated tablets.

15.13 Preparation and storage: Store at room temperature 2°C to 30°C (36°F-86°F). Please see current investigator brochure.

15.14 Administration: Apixaban will be provided in bottles containing 200 tablets of either 2.5 mg or 5 mg.

Administer without regard to meals. If patient is unable to swallow whole tablets whole, 2.5 or 5 mg tablets may be crushed and suspended in water, 5% dextrose in water (D5W), apple juice, or apple puree and promptly administered orally. Crushed apixaban tablets are stable in water, D5W, apple juice and apple puree for up to 4 hours. Tablets may also be crushed and suspended in 60 mL of dextrose 5% in water followed by immediate delivery through a nasogastric tube.

15.15 Appearance:
Study drug allocation will be blinded and could be to either apixaban 2.5 mg dose or 5 mg dose. Both doses will be blinded by the company such that neither the investigator nor the patient will know which tablet strength they are using.

15.16 Pharmacokinetic information:
a) Absorption – Time to peak after oral administration is 3 to 4 hours; bioavailability is approximately 50% for doses up to 10 mg.
b) Distribution – Plasma protein binding in humans is approximately 87%. The steady-state volume of distribution is approximately 21 L.
c) Metabolism – Hepatic predominantly via CYP3A4 and to a lesser extent via CYP1A2, 2C8, 2C9, 2C19, and 2J2; substrate of P-glycoprotein (P-gp) and breast cancer resistant protein (BCRP)
d) Excretion – Urine (27% as parent drug); feces
e) Half-life Elimination – approximately 12 hours

15.17 Potential drug interactions: Apixaban is a substrate of both CYP3A4 and P-gp. Inhibitors of CYP3A4 and P-gp increase exposure to apixaban and increase the risk of bleeding. Inducers of CYP3A4 and P-gp decrease exposure to apixaban and increase the risk of stroke and other thromboembolic events.
Avoid concomitant use with dual strong CYP3A4 and P-glycoprotein inhibitors (eg, clarithromycin, ketoconazole, itraconazole, ritonavir).
Anticoagulants: Apixaban may enhance the anticoagulant effect of other Anticoagulants. *Risk X: Avoid combination*
Combination with fibrinolytics increases the risk of bleeding.
Agents with Antiplatelet Properties (e.g., P2Y12 inhibitors, NSAIDs, SSRIs, etc.) may enhance the adverse/toxic effect of Apixaban. Specifically, the risk for bleeding may be increased. *Risk C: Monitor therapy*
CYP3A4 Inducers (Moderate): May decrease the serum concentration of CYP3A4 Substrates. *Risk C: Monitor therapy*
CYP3A4 Inducers (Strong): May decrease the serum concentration of Apixaban. *Risk X: Avoid combination*
CYP3A4 Inhibitors (Moderate): May decrease the metabolism of CYP3A4

Substrates. *Risk C: Monitor therapy*

CYP3A4 Inhibitors (Strong): May increase the serum concentration of Apixaban. Management: Apixaban U.S. prescribing information states dose reduction criteria that may be applied under some circumstances. See full interaction monograph for details. *Risk X: Avoid combination*

Exceptions: Clarithromycin; Cobicistat; Darunavir; Itraconazole; Ketoconazole (Systemic); Lopinavir; Ombitasvir, Paritaprevir, and Ritonavir; Ritonavir; Saquinavir; Telaprevir. *Risk C: Monitor therapy*.

Inhibitors of CYP3A4 (Strong) and P-glycoprotein: May increase the serum concentration of Apixaban. Management: US labeling recommends a 50% apixaban dose reduction in patients who would otherwise receive 5 or 10 mg twice daily, and avoiding in patients who would otherwise receive 2.5 mg twice daily. Canadian labeling lists any combined use as contraindicated. *Risk D: Consider therapy modification.*

Grapefruit juice may increase levels/effects of apixaban. Management: Advise patients who consume grapefruit juice during therapy to use caution; monitor for increased effects (eg, bleeding).

15.18 Known potential toxicities:

Consult the current investigator brochure for the most current and complete information.

Adverse effects by frequency:

>10%:

Hematologic & oncologic: Hemorrhage (1% to 12%; major: $\leq 3\%$; clinically relevant non-major bleeding: 2% to 4%)

1% to 10%:

Endocrine & metabolic: Increased gamma-glutamyl transferase ($\leq 1\%$)

Gastrointestinal: Nausea (3%)

Hematologic & oncologic: Anemia (3%), bruise (1% to 2%), Post-procedural hemorrhage ($\leq 1\%$)

Hepatic: Increased serum transaminases ($\leq 1\%$)

<1% (Limited to important or life-threatening):

Anaphylaxis, gastrointestinal hemorrhage, hematuria, hemophthalmos, hypersensitivity, hypotension, incision site hemorrhage, increased serum alkaline phosphatase, increased serum AST, increased serum bilirubin, intracranial hemorrhage, muscle hemorrhage, perioperative blood loss, postoperative hematoma (incision site), rectal hemorrhage, syncope, thrombocytopenia, wound secretion

15.19a Drug procurement: Bristol Myers-Squibb will supply apixaban labeled for investigational use to Biologics, Inc.

Each participating ACCRU treating location will order a starter supply of blinded apixaban 5mg/apixaban 2.5mg from Biologics. Fax the Drug Order Request Form (found in the forms packet) to the following:

ACCRU Registration Office personnel will monitor the supply of blinded apixaban at each participating location and will arrange for Biologics to send additional supplies, as needed.

Outdated or remaining drug is to be destroyed on-site as per procedures in place at each institution.

15.19b Nursing guidelines

- Warn patient to avoid taking medication with any other agents (i.e., aspirin, NSAIDS, etc.).
- Warn patients of risk of bleeding, including serious life-threatening internal bleeding.
- Patients may bruise easily. Instruct patients to report excessive bruising to study team.
- Rarely patients may have nausea; treat symptomatically and monitor for effectiveness.
- Patients should be instructed to let all providers know they are taking medication especially prior to any surgical/invasive procedure.
- Patients should be instructed to avoid agents that utilize the CYP3A4 pathway. Instruct patients to contact the study team prior to starting any new medications.
- Rarely LFTs may increase; monitor LFTs per protocol.

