7.3 Breaking Codes in Double-Blinded Studies

The treatment code cannot be broken except in the event of an emergency for an individual patient. In the event of an emergency, call the ACCRU Registration Office at [REDACTED] to break the code on Monday through Friday, 8:00 a.m. to 4:30 p.m.

Central Time. Place a call to the ACCRU Registration Office and leave a message informing them of the need to un-blind a patient. Provide your contact information so that ACCRU Registration Office personnel can return the call the next business day. If a patient has been removed from the study and the clinician believes it is important to know what dose the patient was on, they can be unblinded. Before unblinding, all protocol data should be collected.

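### Appendix II leaves out cobicistat and telaprevir, which 15.17 places among strong CYP3A4 inhibitors, and a monitor-only rating in 15.17 does not match the ban in 3.24, 8.1 and 9.1 (low severity)

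*Combined protocol and SAP*

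**What the plan says.** The operative rules agree with one another. Section 3.24 excludes current users of strong CYP3A4 inhibitors or inducers unless they switch or stop. Section 8.1 requires the interacting drug to be stopped or replaced, and the patient to be removed from the trial if neither is possible. Section 9.1 prohibits concomitant use. Each names the class and refers to Appendix II.

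Section 15.17 is reference material on interactions. It warns that "Inhibitors of CYP3A4 and P-gp increase exposure to apixaban and increase the risk of bleeding". It advises: "Avoid concomitant use with dual strong CYP3A4 and P-glycoprotein inhibitors (eg, clarithromycin, ketoconazole, itraconazole, ritonavir"), where the four drugs are given as examples. Its entry for the class begins "CYP3A4 Inhibitors (Strong): May increase the serum concentration of Apixaban" and carries a Risk X (avoid) rating, followed by "Exceptions: Clarithromycin; Cobicistat; Darunavir; Itraconazole; Ketoconazole (Systemic); Lopinavir; Ombitasvir, Paritaprevir, and Ritonavir; Ritonavir; Saquinavir; Telaprevir" and then a Risk C (monitor) rating.

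The next entry covers drugs that inhibit both strong CYP3A4 and P-glycoprotein. It reports that "US labeling recommends a 50% apixaban dose reduction in patients who would otherwise receive 5 or 10 mg twice daily", that the combination is to be avoided in patients who would otherwise take 2.5 mg, and that Canadian labeling contraindicates any combined use. It is rated "Risk D: Consider therapy modification".

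On blinding, 15.15 says that "neither the investigator nor the patient will know which tablet strength they are using", and 7.3 says: "The treatment code cannot be broken except in the event of an emergency for an individual patient". Section 7.3 also allows unblinding once a patient has been removed from the study.

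**The concern.** Two things do not fit together. First, the list that three operative sections cite is shorter than the set of drugs that the protocol itself treats as strong inhibitors. Someone checking cobicistat or telaprevir finds no entry in Appendix II and a monitor rating in 15.17, so both look-up sources lean towards allowing the drug. Second, for drugs that are on the Appendix II list, 15.17 prints a rating that falls short of the prohibition, and for four of them it contradicts its own advice to avoid.

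At stake is exposure to a combination that may raise apixaban concentration in a patient taking the drug for up to 12 months, in a trial whose primary endpoint is bleeding. This is a matter of patient safety and of consistent screening between sites. No statistical quantity is involved.

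**Working it through.** No arithmetic beyond counting applies, and the plan gives no figure to reproduce. The check sets the ten exception entries in 15.17 against the strong inhibitors in Appendix II and against the avoid line in 15.17.

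Appendix II names 17 strong inhibitors: clarithromycin, telithromycin, nefazodone, itraconazole, ketoconazole, posaconazole, voriconazole, atazanavir, boceprevir, darunavir, delavirdine, indinavir, lopinavir, nelfinavir, ritonavir, saquinavir and tipranavir.

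| Exception entry in 15.17 | In Appendix II? | On the 15.17 avoid line? |
|---|---|---|
| Clarithromycin | by name | named |
| Cobicistat | no | not named |
| Darunavir | by name | not named |
| Itraconazole | by name | named |
| Ketoconazole | by name | named |
| Lopinavir | by name | not named |
| Ritonavir combination product | through ritonavir | through ritonavir |
| Ritonavir | by name | named |
| Saquinavir | by name | not named |
| Telaprevir | no | not named |

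- Appendix II: 7 by name + 1 through a component + 2 absent = 10 entries. So 7 + 1 = 8 entries are barred even if the appendix is taken to limit the ban. If the class wording of 9.1 governs, all 10 are barred.
- Avoid line: 4 drugs named, matching 4 + 1 = 5 entries once the ritonavir combination is counted. Because that line gives examples only, the other five entries are not shown to fall outside it.

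The exceptions can be read in two ways.

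1. As printed, the Risk C rating closes the list of exceptions, so the ten entries are to be monitored. That conflicts with the ban.
2. The exceptions may be meant only to hand drugs on to the following entry on dual inhibitors. That entry is rated Risk D, with dose halving for patients on 5 mg. This is still not the stop, switch or remove rule of 8.1. Its advice also differs between 2.5 mg and 5 mg, so a blinded site cannot apply it.

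Neither rating states the trial's rule. On the second reading, however, the content comes close: any blinded patient may be on 2.5 mg, so a cautious site would arrive at avoidance.

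A caveat applies to the two absences. Appendix II was read from a table with shifted rows: posaconazole and voriconazole appear in the protease-inhibitor row. Nothing suggests that entries were lost, but the absence is established only for the text as extracted.

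**The case against.** The strongest reply is that 15.17 is background and authorises nothing. It describes labeling and refers the reader to a fuller monograph. A site following the eligibility and treatment sections would handle the eight listed entries correctly whatever 15.17 says. For cobicistat and telaprevir, the look-up that shows a monitor rating also shows them under the strong-inhibitor heading, which is the class that 3.24, 8.1 and 9.1 bar. To go wrong, a reader must take the appendix as exhaustive and overlook that heading.

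There are further safeguards. Section 15.19b has patients told to avoid drugs that use the CYP3A4 pathway and to call the study team before starting anything new. The phone script in Appendix V asks about new medications. Section 4.0 schedules a review of selected concomitant medications at baseline, every 30 days and at end of treatment.

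Most of this stands, and it is why the severity is low. What remains is that these steps bring a drug to the site's attention without correcting the list that the site then consults.

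Three stronger readings are tempting, and the documents support none of them:

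- A reader might infer that 15.17 permits these drugs on study, or that absence from Appendix II makes the two missing drugs allowed. The class wording in the operative sections says otherwise.
- A reader might infer that the dose-halving text threatens the blind. No operative section authorises that adjustment, and 7.3 confines code-breaking to emergencies and to patients already removed.
- A reader might infer that the bleeding comparison is compromised. The documents give no count of patients on these drugs and nothing to suggest a difference between arms.

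**Conclusion.** The inconsistency is real and the text is wrong as written, but it is minor. Appendix II as extracted lacks two drugs that 15.17 groups with strong CYP3A4 inhibitors, and 15.17 gives a monitor rating to eight entries that are barred through the appendix. These are counts of list entries and do not measure risk.

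The conclusion rests on two assumptions: that the extracted appendix is complete, and that being listed as an exception under the strong-inhibitor heading means 15.17 regards a drug as a strong inhibitor, which is the natural reading. If the class wording of 9.1 is taken as controlling, leaving out the two drugs is a clerical gap in a list. If a site works from the list alone, it is a gap in screening. Harm is unlikely on either view. Severity: low.

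**What to change.** 1. Add cobicistat and telaprevir to the strong-inhibitor column of Appendix II.
2. In 15.17, mark the Risk C exceptions and the Risk D dose-reduction text as label information that does not apply to blinded study drug. Keep the text: deleting it would also remove the statements on avoiding the combination at 2.5 mg and on the Canadian contraindication, both of which point the same way as the ban.
3. Add one sentence to 15.17: Sections 3.24, 8.1, 9.1 and Appendix II govern all strong CYP3A4 inhibitors and inducers.

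The cost is two drug names and a short wording change, with no new procedures or data and no change to sample size or analysis. The one downside is that any patient on either drug must switch, be excluded or be removed, which the class ban already implies.

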16.0 Statistical Considerations and Methodology

16.1 Sample Size Determination

The primary objective of this study is to determine whether apixaban 2.5 mg twice daily has less bleeding (major bleeding plus clinically relevant nonmajor bleeding) compared to apixaban 5 mg twice daily for secondary VTE prevention in patients with active cancer, previously confirmed deep-vein thrombosis (DVT) or pulmonary embolism (PE) for which they have completed at least 6 months (but no more than 12 months) of anticoagulant therapy. Important assumptions include both clinical and trial observation that bleeding rates in cancer patients with VTE are higher than non-cancer patients. As such, a recent meta-analysis of cancer patients treated with direct factor inhibitors showed that rates of major bleeding were 3.2% and clinically relevant non-major bleeding 14.5% (19). This would equate to rates of 17.7% for these combined outcomes.

The trial is designed as a two-arm, double-blind, randomized study. Patients will be randomized at a 1:1 ratio to receive either 5 mg or 2.5 mg of apixaban twice daily. Assuming the combined bleeding event rate is 9% in the 2.5 mg arm, and 18% in the 5 mg arm, a sample size of 352 (176 per arm) will give us approximately 70% power to detect a difference between the two arms (using a two-sample comparison of proportions with a two-sided alternative at a 5% significance level). The sample size is inflated by 5% to a total of 370 (185) to account for ineligibility and cancellation. We anticipate accruing 15 patients per month to this trial. Based on this accrual rate, we anticipate the trial will complete accrual in 24 months. With the last patient accrued followed for 12 months, the primary analysis will be conducted approximately 36 months after the trial opening. The sample was calculated using EAST 6.3 (Cytel Inc.).

16.2 Primary Hypothesis:

We hypothesize that apixaban 2.5 mg twice daily is associated with a significantly lower combined rate of major bleed plus clinically relevant nonmajor bleed compared to apixaban 5 mg twice daily for the secondary prevention of VTE in patients with active cancer and confirmed deep-vein thrombosis (DVT) or pulmonary embolism (PE) who have completed at least 6 months (but no more than 12 months) of anticoagulant therapy.

16.21 Primary Safety Analysis:

All patients who received at least one dose of either apixaban 2.5 mg or apixaban 5 mg will be included in the primary analysis. Patients will be analyzed according to the drug they received because this is a safety analysis rather than an efficacy analysis. The analysis of major bleeding plus clinically relevant nonmajor bleeding events will primarily focus on those events which occurred during treatment or within 7 days of treatment discontinuation. Major bleeding events observed later will be described separately.

It should be noted that this study is powered for our primary analysis, in which the proportion of patients experiencing at least one bleeding event within 12 months of beginning treatment will be compared across the two study arms using a two-sample comparison of proportions with a one-sided alternative at a significance level of 5% (i.e. a “Z” test).

Though **not part of the primary analysis**, a number of additional analyses of the primary endpoint will also be performed to further explore the data. These should be viewed as additional secondary analyses. In particular, frequency of major bleeding and clinically relevant non-major bleeding will be tabulated by treatment arm. Incidence of major bleeding and clinically relevant non-major bleeding will be estimated using the cumulative incidence function with death without major bleeding or clinically relevant non-major bleeding and with adverse events that results in termination of treatment (including vascular events) as competing risks. The time to event is defined as the time from randomization to the first occurrence of a major bleeding, a clinically relevant non-major bleeding, death without major bleeding or clinically relevant non-major bleeding, or an adverse events that results in termination of treatment (including vascular events). Patients who were lost to follow-up, who withdrew informed consent before the end of the predefined study duration will be censored at the last day the patient had a complete assessment for study outcomes within the intended

study period. The incidence curves of major bleeding and clinically relevant non-major bleeding will be plotted. The incidence of major bleeding and clinically relevant non-major bleeding will be summarized as a combined endpoint and separate endpoints by treatment arm. The difference in the incidences of the combined endpoint at 6 months and at 12 months between treatment arms will be estimated and tested using a normal approximation of the binomial distribution. All tests will be conducted at the one-sided 0.05 significance level.

The incidences of death due to cancer or other causes (without major bleeding or clinically relevant non-major bleeding) and adverse events that result in termination of treatment will be estimated and compared using the same approach.

A sensitivity analysis for these endpoints will be conducted using a stratified (by stratification factors listed in Section 5.0) Cox model adjusting for baseline covariates including location of DVT, renal clearance, age, sex, mobility at randomization, pulmonary disease, and cardiac disease.

16.22 Secondary Safety Analysis:

A secondary safety analysis of the primary safety endpoint will be performed on an intent-to-treat basis using the same approach described in Section 16.21. In addition, we will compare proportion of patients who experience at least one bleeding event (i.e. the primary endpoint) within 6 months of beginning treatment across the two study arms. As with the primary analysis, this will be done using a two-sample comparison of proportions with a one-sided alternative at a significance level of 5%.

16.23 Secondary Efficacy Analysis:

For the secondary efficacy analysis, the time to the first event of the composite DVT/PE outcome will be analyzed using the same method described in Section 16.21. For this outcome, death without DVT/PE and adverse events leading to termination of treatment will be treated as the competing risks.

16.3 Handling of Missing Data:

Monitoring and auditing procedures should be followed, in order to comply with Good Clinical Practice (GCP) guidelines. Each center will be audited at regular intervals to ensure compliance with the protocol, GCP and legal aspects. This will include on-site checking of the CRF for completeness and clarity, cross-checking with source documents, and clarification of administrative matters.

16.4 Interim Analysis and Study Monitoring:

No formal interim analysis is planned. Risk-benefit will be evaluated by the Mayo Clinic Data Safety and Monitoring Board (DSMB), which will give regular recommendation to the executive committee. Early termination of accrual will be considered if there is evidence of a significant difference in major bleeding rates between the comparators. Access to interim tabular risk benefit data will be restricted.

16.5 Adverse Event Stopping Rule:

The stopping rule specified below is based on the knowledge available at study development. We do note that the Adverse Event Stopping Rule may be adjusted in the event of either (1) the study re-opening to accrual or (2) at any time during the conduct of the trial and in consideration of newly acquired information regarding the adverse event profile of the treatment(s) under investigation. The study team may choose to suspend accrual because of unexpected adverse event profiles that have not crossed the specified rule below.

Accrual will be temporarily suspended to this study if at any time we observe events that the study team considers to be at least possibly related to study treatment (i.e., an adverse event with attribute specified as “possible,” “probable,” or “definite”) that satisfy the following:

- If 5 or more patients in the first 20 treated patients of either of the study arms (or 20% of all patients after 20 are accrued) experience a grade 4 or higher non-hematologic adverse event.

We note that we will review grade 4 and 5 adverse events deemed “unrelated” or “unlikely to be related” to verify their attribution and to monitor the emergence of a previously unrecognized treatment-related adverse event.

